Training will use Stanley and Brown's well-established methods for videoconference training. SPI and C-SSRS training take about 6 hours total. Prior to the training, individuals will be emailed the SPI manual used in a previous intervention trial (SPIRIT).^{29,46} On the day of the training, information on the rationale for SPI, an overview of SPI, and the steps of SPI, with video clip demonstrations interspersed will be presented. We will provide an additional 30 minutes of training in reaching out to and re-engaging justice-involved individuals in BH care. After completing the online training and study of the written SPI manual, counselors will receive a 2.5 hour live training in SPI fidelity rating via webcam (i.e., it is live, but not in person). The group views and rates fidelity of SPI videos that vary in quality, and then discusses their answers. Drs. Stanley and Brown have found that practicing SPI fidelity assessment by critiquing SPI helped learners understand the SPI model and commit it to memory. C-SSRS training also includes video and live practice. These trainings will be recorded to ensure fidelity and consistency across the trainings. The audio/video files recorded during the meeting will be downloaded onto secure servers at Butler and Michigan State University (MSU).

Weekly reports: During the months BH agencies are assigned to the RRT intervention condition, they will receive weekly reports from CareSource with notifications of jail booking/release dates of any client seen by the agency in the 6 months prior to arrest. Reports will include instructions for how to reengage the client, and a reminder that the C-SSRS can be used for suicide risk assessment. Subscribers with any past (lifetime) suicide attempt documented in available claims data will be flagged for additional outreach and action, including SPI. These reports will be built into an existing, automated CareSource system that

sends jail booking/release data to BH agencies. This system is currently being piloted and refined by CareSource.

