RRT Fidelity. We will be able to electronically track whether reports go out and whether they are timely/accurate. In addition, although we do not have a scalable way to track outreach attempts for 6,000 subscribers in Study 2, we will carefully document implementation processes and meet monthly with CareSource and intervention agencies, hear their experiences, offer feedback, and help problem-solve challenges. We will keep structured implementation process notes from these meetings for further analysis. Provider names will be included in the notes. All data from the implementation process feedback will be securely stored in REDCap. No names or identifiers will be used in any published works and will be accessible only to authorized research staff. Testing our service engagement mechanism will also help to elucidate steps in the causal chain (i.e., from the reports, to services provided, to suicide attempts).

Assignment to “intervention” and “control” conditions in the two studies is independent: participants may receive Intervention-Intervention, Intervention-Control, Control-Intervention, or Control-Control. Participants will be followed for 6 months following jail release using claims data.

C4. Data Analysis

Twelve months of historical (i.e., prior to arrest) and six months of prospective (i.e., after release) jail and Medicaid claims data will be extracted from CareSource’s Jail-Medicaid database for each participating subscriber for all measures, including demographics, diagnoses, suicide attempts, service use, number of arrests, dates of jail bookings/releases, and days incarcerated. Each eligible subscriber will be followed for 6 months following the index release from jail using claims data. CareSource will provide a limited dataset to the P50 Center (at MSU) that will be de-identified and analyzed by Center statisticians. Because these statisticians are employed by Brown University, an IAA will be established with both MSU and Brown University.

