For Aim 1, we will assess total number of subsequent attempts using the already-developed Mental Health Research Network (MHRN) algorithm for extracting MT suicide attempt information from claims data.^{10-12,48-58} The main effectiveness analysis is planned as a comprehensive model (i.e., including all 43,000 subscribers) evaluating Study 1 and Study 2 intervention effects, which provides optimal power and the ability to test interactive effects of interventions. All analyses will covary baseline (i.e., past year) values of dependent variables, and will use days incarcerated in the 6 months after the index jail release as an offset. **MT suicide attempts.** The main analysis framework will be logistic regression with the cumulative risk of a claims-data-identified suicide attempts requiring medical treatment over six months post-release as the outcome. We will secondarily use a negative binomial model and a count outcome for the number of MT suicide attempts. Our models will include robust standard errors due to clustering at the agency level. We will adjust for study month, and include indicator variables reflecting: (1) Study 1 intervention condition (i.e., CC or CAU); (2) inclusion in Study 2; (3) Study 2 intervention condition (i.e., RRT or Control). The ***hypothesis that the Study 1 intervention (CC) reduces suicide attempts*** is evaluated with magnitude and significance of parameter estimate associated with random assignment to the Study 1 intervention. The ***hypothesis that the Study 2 intervention (RRT) reduces suicide attempts*** is tested with the parameter estimate associated with exposure to the level 2 intervention. ***The hypothesis that the addition of flags and recommendations to provide SPI*** for individuals with past 12 months claims data identified suicide attempts (one component of the Study 2 intervention) ***will further reduce suicide attempts*** will be tested through the interaction between past history of suicide attempt and being in the Study 2 intervention condition. Identical analyses will be conducted for the other outcomes (all count outcomes): all cause injury and poisoning, outpatient BH visits, calls to CMS line, suicide-related ED visits/hospitalizations, and returns to jail detention. ***Exploratory.*** We will evaluate the interaction of Study 1 and Study 2 interventions by including an interaction term of the two indicators. ***Moderators.*** We will test sex, race/ethnicity, past suicide attempt (y/n), past 6-month BH visit (y/n), past 12-month arrest (y/n), area Deprivation Index,⁵⁹⁻⁶⁰ Mental Health Professional Shortage Area (HPSA)

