For focus groups/implementation process notes (for which we have identifiable data), the PIs will ensure that information on any adverse effects on provider participants are reported to the IRB/DSMB. If any unanticipated problems are detected, these will be submitted to the respective IRBs and DSMB within 72 hours. The Principal Investigators will be responsible for tracking these reports and relaying them as required to their IRBs.

For Caring Contacts and RRT, CareSource will provide a limited datafile to P50 Center statisticians who will generate a de-identified analytic dataset with aggregated, clinic-level data that will be used by the study team to analyze study findings. Similar to studies conducted in the Mental Health

Research Network, service connection and suicide-related outcomes for these 43,000 individuals are evaluated through claims data. Standard reporting and monitoring “adverse events” as typically defined (i.e., patient death, hospitalization, etc.) in real time is not possible because: (1) claims data lag, and (2) data are aggregated and de-identified. However:

1. All study interventions are either standard of care (reach out to individuals after jail release to see if they need additional mental health or substance use treatment) and we are providing a systematized way to do it (through Caring Contacts or weekly reports to agencies) or are considered suicide prevention best practices (assessment with the C-SSRS and intervention with SPI, the only evidence-based suicide prevention intervention for the target population). Therefore, it seems appropriate to evaluate aggregate outcomes of these system-level efforts to use evidence-based practices.
2. Study interventions take place over 12 months. Because of the lag in claims data (~3 months) and the need to de-identify and integrate datasets to be sent to the PIs, it is not possible for us to have real-time access to the data. However, we will take two steps to provide safety information to the DSMB in a timely way:
 - a. We will have the Data and Safety Monitoring Board (DSMB) review the study prior to the start of the study, and then review extant safety data at 6, 9, and 12 months after the start of the study.

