 - b. CareSource estimates that about half of their claims are submitted within 30 days of the service date. Adding time to clean and de-identify the data, run the MHRN algorithm on the data, and prepare the DSMB report, we estimate that about half of claims data will be available for safety review within 60 days of the service date. Therefore, at Month 6, the DSMB will have all the cases from Months 1-3, and half of the cases from Month 4 for review. At Month 9, the DSMB will have all the cases from Months 1-6 and half of the cases from Month 7 for review. At Month 12, the DSMB will have all the cases from Months 1-9, and half the cases from Month 10 for review. Then, the DSMB will have a closeout meeting when all study data are available.

Analyzed participant data will be stripped of personal information by CareSource, and will be identified in the project only by numerical codes. Links between these codes and personal identifiable information (e.g. names) will only exist in the CareSource database (which will not be accessible by research staff). The collected data will be stored on secure servers at Butler and MSU, which are consistently used for data hosting needs. The outcomes of interest will include suicide attempts, engagement with outpatient mental health and substance use services, and returns to jail detention. We will report pre-post intervention changes in the outcomes, both unadjusted, and adjusted for participant characteristics

Most data collected during the study timeframe will be entered into an online data management system (REDCap). Data will be stored on backed up, password protected servers. Within each computer system, only those users authorized to access the data for a given study are able to do so.

Data from focus groups and provider meetings will also be shared with the DSMB. Since no adverse effects are anticipated from these participant groups, any significant negative feedback from these participants will be shared with the DSMB.

Data and Safety Monitoring Board (DSMB)

This project will utilize the central Center DSMB. Our analysis plan will be reviewed and approved formally by the DSMB prior to the start of the study.

E. Potential Benefits

There are no direct benefits from participation in this study, but there are potential benefits.

Participating providers will have the opportunity to be trained in how to address suicide risk assessment

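### SPI flags use claims in hand at the weekly report, but the flag test very probably uses claims that arrive later: modest dilution, cheaply addressed by archiving the weekly query

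*Combined protocol and SAP*

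**What the plan says.** Section C2, Weekly reports: while an agency is in RRT, "they will receive weekly reports from CareSource" giving "notifications of jail booking/release dates of any client seen by the agency in the 6 months prior to arrest". On the flag, the same paragraph says: "Subscribers with any past (lifetime) suicide attempt documented in available claims data will be flagged for additional outreach and action, including SPI".

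Section D3 (Data Safety Monitoring Plan) describes how fast claims arrive: "CareSource estimates that about half of their claims are submitted within 30 days of the service date". It puts the overall lag at about 3 months and works through what the DSMB will be able to see at Months 6, 9 and 12.

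Section C4 (Data Analysis) describes the analysis data: "Twelve months of historical (i.e., prior to arrest) and six months of prospective (i.e., after release) jail and Medicaid claims data will be extracted". Study 2 inclusion enters the model as an indicator. The hypothesis about adding flags, worded for people with an attempt in the past 12 months, "will be tested through the interaction between past history of suicide attempt and being in the Study 2 intervention condition".

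**The concern.** The flag can reflect only the claims that have reached CareSource when the report is made. The test of the flag relies on attempt history in the analysis extract. That extract runs to six months after release, so it cannot be complete until claims from before the arrest have had more than the stated lag to arrive. Someone whose attempt was shortly before arrest may therefore be analysed as a past attempter under RRT, and so as flagged, although no attempt claim was visible at the report.

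The plan works the lag through for safety review but not for the flag or the report listing. No variable in the model records whether a flag was sent or could have been sent. At stake is how the interaction is read: a weak result could mean that the flag does little, or that it was not sent to some of the people counted as having it. The people most affected are those with the most recent attempts.

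**Working it through.** **The plan's own figure.** The Statistical power paragraph of C4 gives 96.4% power for an odds ratio (OR) of 0.63 in Study 2 subscribers with a past-year attempt. Cohorts start at Months 4, 6, 8 and 10 of 12, so agencies are exposed for 9 + 7 + 5 + 3 = 24 of 48 cohort-months. About 300 of the 600 expected past attempters are then exposed. A plain two-group comparison of 300 v 300 (0.204 v 0.139, two-sided 5%) gives 56%, so 96.4% is not reproduced. The plan's figure comes from a simulation whose code is not given. That gap is a separate matter, and the shares below do not depend on it.

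**Inputs from the documents.** Half of claims by day 30 and a lag of about 3 months (D3); weekly reports (C2); jail stay with mode 2 days and median 36 days (section B); six-month risk 0.204 with a past-year attempt, OR 0.63 for flagged clients and 0.87 for RRT (C4).

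**Assumptions.** Claims arrive linearly, 50% by day 30 and 100% by day 90. Attempt claims arrive as fast as other claims. There is one report, on average 3.5 days after release, with no added processing time. The person has no older attempt claim.

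**Share not visible.** At t days after service the missing fraction is m(t) = 1 − t/60 up to day 30, then (90 − t)/120 up to day 90. For an attempt s days before arrest, t = s + stay + 3.5.

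- 2-day stay, from t = 5.5: the integral of m is [24.5 − (900 − 30.25)/120] + 15 = 17.25 + 15 = 32.25 days.
- 36-day stay, from t = 39.5: the integral is 50.5²/240 = 10.63 days.

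| Past-year attempters with no visible claim | 2-day stay | 36-day stay |
|---|---|---|
| Attempts even over 365 days | 32.25/365 = 8.8% | 10.63/365 = 2.9% |
| Half of attempts in the last 90 days | 0.5 × 32.25/90 = 17.9% | 0.5 × 10.63/90 = 5.9% |
| Attempt in the last 30 days only | 19.88/30 = 66% | 8.875/30 = 30% |

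Of 300 exposed past attempters, the first row is about 27 or 9 people and the second about 54 or 18.

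**Other lag shapes.** Other arrival patterns that keep half of claims by day 30, with a report 3.5 days after booking and even attempts, give 3.6% to 15.5% (base 9.4%). For attempts in the last 30 days they give 44% to 94% (base 69%). At 36 days after booking the past-year share is 0% to 7.4% (base 3.3%).

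**Effect on the odds ratio.** OR 0.63 on a risk of 0.204 gives 0.139. With a share u missed, the RRT risk is (1 − u) × 0.139 + u × r. Here r = 0.204 if missed clients gain nothing, or 0.182 if they still get the RRT effect of 0.87.

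| u | OR, missed gain nothing | OR, missed get 0.87 |
|---|---|---|
| 2.9% | 0.640 | 0.637 |
| 5.9% | 0.650 | 0.644 |
| 8.8% | 0.660 | 0.650 |
| 17.9% | 0.692 | 0.671 |

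**Effect on power.** Take 96.4% at face value and scale its noncentrality, 1.80 + 1.96 = 3.76, by ln(OR)/ln(0.63). At 10% missed with no benefit the OR is 0.664 and power is about 91%. At OR 0.692, 3.76 × 0.797 − 1.96 = 1.04, or about 85%. On the 300 v 300 approximation, 10% missed takes power from 56% to 47%.

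**Report listing.** One processed visit in the six months (182 days) before arrest puts a client on the report. For a 2-day stay and evenly spread, independent visits, the chance of being missed is 32.25/182 = 17.7% with one visit, 0.177² = 3.1% with two and 0.177³ = 0.6% with three.

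**The case against.** Several points on the other side stand.

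- The plan does not say that past attempt or Study 2 inclusion is set from later, complete claims. It gives no as-of date. Later claims are a strong inference from the extract window, not a stated rule.
- The flag covers any lifetime attempt in available claims, so an older processed claim triggers it even when the latest claim is outstanding. Reports are weekly, and nothing says a client can be flagged only once. Under the lag model used, the shares above are therefore upper figures. It would be wrong to say that the missed clients could never have been flagged.
- A listed but unflagged client still gets outreach, a C-SSRS reminder and SPI-trained providers, so the right-hand OR column is a fair alternative.
- Even the largest shift, 0.63 to 0.69, is 0.09 on the log scale, against a standard error of about 0.22 for 300 v 300.
- Imperfect flagging is part of the real-world effect of a claims-triggered flag. C4 already expects that some providers will not deliver SPI.

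A reader might infer bias in favour of RRT, with recent attempters kept in control months but lost from RRT months. That would need sent reports to define RRT months and claims to define control months. Nothing proposes this: C4 describes one extraction for every subscriber.

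What remains is that C4 makes a claim about flags, and the RRT Fidelity paragraph of C2 wants to trace the causal chain from the reports onward. Neither can be read cleanly without knowing what was visible. Report tracking covers reports that go out, so it has no counterpart for control months. The measures listed for extraction do not name claim receipt dates or flag status. A later rebuild may be possible, but it is not provided for.

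**Conclusion.** The timing mismatch holds, and its size is modest. Under the stated assumptions about 3–9% of past-year attempters would be analysed as flagged without an attempt claim visible at the report, or 6–18% if half of attempts fall in the last 90 days. That second recency pattern is an assumption with no source in the documents. The OR of 0.63 becomes about 0.64–0.69, or 0.64–0.67 if missed clients still get the RRT effect.

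A reader might infer that many past attempters overall go unflagged. The figures support that only for attempts in the 30 days before arrest (30–66%). A reader might also infer that the reported and analysed Study 2 populations differ materially; for clients with more than one visit they hardly do. Because late claims define the subgroup in the same way in RRT and control months, the consequence is dilution toward no effect and not confounding.

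A related inconsistency must be settled with it. The flag rule is lifetime, while the hypothesis and the extract use 12 months, so some people with only older attempts would be flagged but analysed as non-attempters.

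**What to change.** 1. From Month 1, run the automated weekly query for all 12 agencies and send it only to agencies in RRT. Archive each run with its claims cut-off date, whether an attempt claim was visible, and that claim's service date.
2. For the SPI test, define Study 2 inclusion and past attempt from claims visible at the first report after the index release, identically in RRT and control months. Keep the stated 12-month window for the hypothesis group, and do not let the archived flag silently turn it into a lifetime group.
3. Reconcile the 12-month hypothesis in C4 with the lifetime flag rule in C2. The archived service date allows either window to be applied.
4. Report the complete-claims version alongside as a sensitivity analysis, and give the share of past-year attempters actually flagged.

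The cost is storing the query for control agencies as well, and a short addition to C4. The flagged group becomes slightly smaller, because some of the most recent attempters move to the unflagged group; the sensitivity analysis keeps them in view.

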This proposal involves two studies of evidence-based suicide prevention practices triggered by CareSource justice notifications, in a 2x2 factorial design. The **first study** will randomize CareSource's ~43,000 Ohio subscribers who pass through jails over 12 months to receive monthly Caring Contact letters sent by CareSource over a 6-month period or to Care as Usual. The **second study** (running simultaneously) will involve a subset of ~6,000 of the 43,000 subscribers passing through jail who were seen in one of 12 large BH agencies in the 6 months prior to jail detention. Using a stepped wedge design, the 12 agencies will be brought online over time, receiving (a) notifications of jail detentions/releases with instructions for re-engaging clients in services; and (b) training in the Safety Planning Intervention plus notification to use it when a subscriber with past *medically treated* suicide attempts (identified by CareSource through claims data) is released from jail.

Specifically, we plan to examine the following:

Aim 1: Evaluate the effectiveness of the implemented study interventions.

Hypothesis 1a: CareSource subscribers who receive CC letters during the 6-month period will have fewer claims related to suicide attempts than subscribers who did not receive CC letters.

Hypothesis 1b: Provider involvement in the reports, re-engagement, and training (RRT) intervention will be associated with a reduction in subscriber claims related to suicide attempts. Further, the addition of flags and recommendations to provide SPI for individuals with past 12 months claims data identified suicide attempts will further reduce suicide attempts.

Aim 2. Examine the number of outpatient behavioral health claims in the 6 months following the index jail release and number of calls to CMS line as mediators of the intervention/s effects on suicide attempts. Mediation will be revealed by the extent to which the intervention effect parameter estimates change with the addition of the putative mediator. We will use bootstrap methods to estimate 95% uncertainty intervals around the mediated effect.

Aim 3. Examine intervention cost-effectiveness and return on investment. We will examine costs (and savings) in future years for both the Caring Contacts and Reports, Re-engagement, and Training (RRT) components of the proposed study.

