Following notification of jail release, CareSource will mail CC letters to subscribers randomized to CC (~21,500) monthly for 6 months after jail release. CC involves sending individuals at risk for suicide brief, non-demanding messages of care.^{26,34,45,46} Messages: (1) include a simple expression of care or concern; (2) are non-demanding; and (3) include a reminder of available resources/ways to connect with care. CCs in this study will be addressed from and refer to CareSource's Care Management team via the care management service (CMS) line. This team, who works with individuals to arrange appointments with appropriate providers and other relevant resources (including crisis lines). Individuals who are re-arrested during the 6-month follow-up period will continue to receive letters, but will not be re-randomized.

Caring Contacts fidelity: CC letters sent, the dates they were sent, and any letters returned will be tracked using CareSource's automated mailing system. Since the mailing system is automated, it should involve minimal human error or noncompliance.

Study 2: Reports, re-engagement, and training (RRT)

RRT Intervention will involve 120 BH providers who provide services at 12 of the largest BH agencies in Ohio (10 providers per agency). These agencies serve ~6,000 of the 43,000 CareSource subscribers who passed through jail in the 6 months prior to detention. Providers who consent to participate in the RRT Intervention will receive: (a) notifications of jail release for their clients, (b) instructions for re-engaging these clients in services and training in suicide risk assessment to use at re-engagement; and (c) training in SPI plus notification to use SPI when a client with past suicide attempts is released from jail. Suicide attempts for this proposal will primarily refer to medically-treated (MT) suicide attempts (i.e., presented

to ED/hospital for treatment following a suicide attempt) as these are the only types of attempts we can identify through claims data.

Site Interviews: The primary contacts at each of the participating BH agencies will participate in the site interviews. These will be conducted virtually and will be recorded. Audio/video files recorded during the meeting will be downloaded onto secure servers at Butler and Michigan State University (MSU).

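### The SPI flag covers any lifetime attempt in one section and past-12-month attempts in others; unless the interaction moderator matches the flag, older attempters may be coded as unflagged

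*Combined protocol and SAP*

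**What the plan says.** The flag is described in four ways in the combined protocol and SAP.

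- **Lifetime.** Section C2, Weekly reports: "Subscribers with any past (lifetime) suicide attempt documented in available claims data will be flagged for additional outreach and action, including SPI". The reports go out only under RRT: "During the months BH agencies are assigned to the RRT intervention condition, they will receive weekly reports".
- **Past 12 months.** Section A, Hypothesis 1b expects that adding flags and SPI recommendations "for individuals with past 12 months claims data identified suicide attempts will further reduce suicide attempts". The matching clause in section C4 (Aim 1) uses the same window.
- **Past year.** Section C4, Statistical power, identifies Study 2 subscribers with a past-year attempt as those who will be flagged.
- **No window.** The design paragraph in section A speaks only of past medically treated "suicide attempts (identified by CareSource through claims data) is released from jail". The RRT Intervention paragraph in C2 promises "notification to use SPI when a client with past suicide attempts is released from jail".

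Section C4 tests the SPI part of Hypothesis 1b through the interaction of attempt history with Study 2 condition. Neither that term nor the past-attempt entry in the moderator list has a window, although neighbouring moderators do. The extract reaches back twelve months before arrest, "for each participating subscriber for all measures, including demographics, diagnoses, suicide attempts, service use". The baseline covariate is also one year: "All analyses will covary baseline (i.e., past year) values of dependent variables". No section mentions a flag-eligibility variable.

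**The concern.** An interaction needs its moderator defined the same way in both conditions, and here it should identify the people who were, or would have been, flagged. If the flag looks back further than the analysis data, someone whose only attempt is older than twelve months is flagged for SPI under RRT but analysed as unflagged. Report tracking would not repair this by itself, because control-period releases generate no reports.

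Flagged people would then sit on both sides of the contrast. If SPI helps them, the reference group's RRT effect looks stronger and the estimated extra benefit of the flag looks smaller. At stake is the test that section C4 names for the second sentence of Hypothesis 1b.

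**Working it through.** **1. The plan's own figures.** The power section gives 96.4% for OR 0.63 in past-year attempters. A direct two-proportion calculation (300 v 300, risk .204 v .139, two-sided 5%) gives 56.0%. The simulation model is not described, so the 96.4% is not reproduced but is not shown to be wrong. Nothing below depends on it. The risk mix nearly reproduces: 0.9 × .034 + 0.1 × .204 = .051, against .05. The pair .034 and .204 gives OR 7.3, not the stated 5.

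**2. What the ~600 means.** If .05 is the Study 2 average, the past-year share is (.05 − .034)/(.204 − .034) = 9.4%, or 565 of 6,000. Allowing for rounding of .05 (.045 to .055), it is 388 to 741. So the ~600 could be past-year attempters only, or everyone with any past attempt.

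**3. Inputs for an illustration.**
- From the power section: N = 6,000; past-year risk .204; others' average risk .034; OR 0.63 if flagged.
- From C2: cohorts start at months 4, 6, 8 and 10. Over an assumed 12 months with equal cohorts this gives 9, 7, 5 and 3 RRT months, so half of releases are under RRT.
- Assumed: number of older-only attempters, their risk (.034 to .15), and full response (OR 0.63).
- The unflagged OR is ambiguous. The power section gives 0.87 as the Study 2 effect. If 0.87 is the unflagged effect, the true ratio of ORs is 0.63/0.87 = 0.724. If it is the overall effect, the control risk .051 becomes .0447 under RRT. Removing the past-year part (0.1 × .139) leaves .0308/0.9 = .0342, which against .034 is an OR of about 1.0 and a true ratio of about 0.63.

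**4. Formula.** Keep the non-past-year average at .034, apply each subgroup's OR, average the resulting risks, and convert back to an OR for the coded-unflagged group. Diluted ratio = 0.63 / that OR. Loss = 1 − ln(diluted ratio)/ln(true ratio).

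**5. Example (largest case, unflagged OR 0.87).** 600 past-year attempters plus 600 older-only at risk .15.
- Remainder risk: (5,400 × .034 − 600 × .15)/4,800 = .0195.
- Under RRT, .15 becomes .1001 and .0195 becomes .0170.
- Average: (600 × .1001 + 4,800 × .0170)/5,400 = .0262.
- OR v .034 = 0.7655; diluted ratio 0.63/0.7655 = 0.823.
- Loss = 1 − (0.195/0.323) = 39.7%.

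**6. Results.**

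| Older-only people | Risk | Ratio (loss), unflagged OR 0.87 | Ratio (loss), unflagged OR 1.0 |
|---|---|---|---|
| 30 within the ~600 | .034 | 0.725 (0.48%) | 0.631 (0.45%) |
| 300 within the ~600 | .15 | 0.768 (18.3%) | 0.685 (18.0%) |
| 180 besides 600 | .034 | 0.731 (2.9%) | 0.638 (2.7%) |
| 600 besides 600 | .034 | 0.747 (9.7%) | 0.657 (9.2%) |
| 600 besides 600 | .10 | 0.792 (27.6%) | 0.713 (26.8%) |
| 600 besides 600 | .15 | 0.823 (39.7%) | 0.757 (39.8%) |

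If older attempters respond only partly (OR 0.74, unflagged 0.87), the loss with 180 to 600 additional people is 1.6% to 19.5%. If SPI adds nothing in them, there is none.

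**7. Power.** With 600 past-year attempters, no dilution and no clustering, interaction power is about 22% if the unflagged OR is 0.87 and about 41% if it is 1.0. Neither is a figure from the documents.

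**The case against.** The strongest reply is that no misclassification is established. The moderator has no stated window, the list of extracted measures is not exhaustive, and CareSource both builds the flag and prepares the data, so it could supply a lifetime indicator. The operating flag could also be twelve months. All of this stands, and so the concern is conditional. A reader might infer that older attempters will certainly be miscoded; the documents do not say so. They also do not say which rule operates, and they promise no flag variable for control periods.

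A second reply is that Hypothesis 1b names past-12-month attempters, so a 12-month interaction validly asks whether RRT works differently in them. That also stands: the bias exists only when the term is read as flagged versus unflagged, which is how the plan uses it. Even then it is not a pure SPI contrast, because RRT providers are trained in SPI whoever is flagged.

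Third, the contrast for which the power section gives a figure, the effect within past-year attempters, is untouched. That is correct. A reader might also infer that the trial's main results are compromised; they are not.

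Finally, every input on older-only attempters is assumed, and lifetime is limited to available claims, whose depth is not stated. There may be few such people.

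**Conclusion.** The sections contradict one another on who is flagged, and the analysis moderator is not tied to the flag. The interaction is diluted if two conditions hold together: the lifetime rule operates, and no longer look-back indicator reaches the analysts for both RRT and control periods. The direction is toward the null, in proportion to how well SPI works in older attempters.

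The assumed range of loss, about 0.5% to 40% of the log interaction, is nearly the same under either reading of 0.87. The upper end needs 600 additional people, risk .15 and full response all at once. No single power figure for the interaction should be quoted, and its limited power is not cured by correcting the moderator. The point is confined to this one interaction, but it is cheap to settle before the data are extracted.

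**What to change.** 1. Reconcile Hypothesis 1b and the design paragraph in section A, the RRT Intervention and Weekly reports paragraphs in C2, and the extract, interaction and power text in C4 to one flag window and one date from which it counts back. This review chooses neither.
2. Define the interaction moderator by that same rule, derived identically for control and RRT periods.
3. State which window the ~600 in the power section refers to.
4. If the window is twelve months back from arrest, the planned extract suffices and the change is wording only.
5. If the window is longer, or runs to release (so that it includes the detention interval, which the extract as described does not cover), have CareSource export one yes/no flag-eligibility column for all of the roughly 6,000 Study 2 subscribers, control-period releases included. Keep past-year attempts as the baseline covariate and report the 12-month moderator as a sensitivity analysis.

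Cost: at most one extra data column and one sensitivity analysis.
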